5.3.5.6 Abnormal Vital Sign Values

Not every vital sign abnormality qualifies as an adverse event. A vital sign result must be reported as an adverse event if it meets any of the following criteria:

- Is accompanied by clinical symptoms
- Results in a change in study treatment (e.g., dosage modification, treatment interruption, or treatment discontinuation)
- Results in a medical intervention or a change in concomitant therapy
- Is clinically significant in the investigator's judgment

It is the investigator's responsibility to review all vital sign findings. Medical and scientific judgment should be exercised in deciding whether an isolated vital sign abnormality should be classified as an adverse event.

If a clinically significant vital sign abnormality is a sign of a disease or syndrome (e.g., high blood pressure), only the diagnosis (i.e., hypertension) should be recorded on the Adverse Event eCRF.

Observations of the same clinically significant vital sign abnormality from visit to visit should only be recorded once on the Adverse Event eCRF (see Section [5.3.5.4](#) for details on recording persistent adverse events).

5.3.5.7 Abnormal Liver Function Tests

The finding of an elevated ALT or AST ($>3 \times \text{ULN}$) in combination with either an elevated total bilirubin ($>2 \times \text{ULN}$) or clinical jaundice in the absence of cholestasis or other causes of hyperbilirubinemia is considered to be an indicator of severe liver injury (as defined by Hy's Law). Therefore, investigators must report as an adverse event the occurrence of either of the following:

- Treatment-emergent ALT or AST $>3 \times \text{ULN}$ in combination with total bilirubin $>2 \times \text{ULN}$

- Treatment-emergent ALT or AST $>3\times$ ULN in combination with clinical jaundice

The most appropriate diagnosis or (if a diagnosis cannot be established) the abnormal laboratory values should be recorded on the Adverse Event eCRF (see Section 5.3.5.2) and reported to the Sponsor immediately (i.e., no more than 24 hours after learning of the event), either as a serious adverse event or an adverse event of special interest (see Section 5.4.2).

5.3.5.8 Deaths

For this protocol, mortality rate is a safety endpoint. All deaths that occur during the adverse event reporting period, regardless of relationship to study drug, must be recorded on the Adverse Event eCRF and immediately reported to the Sponsor (i.e. no more than 24 hours after learning of the event; see Section 5.4.2). The *i*DMC will monitor the frequency of deaths from all causes.

When reporting a death, the event or condition that caused or contributed to the fatal outcome should be recorded as the single medical concept on the Adverse Event eCRF. Generally, only one such event should be reported. If the cause of death is unknown and cannot be ascertained at the time of reporting, "**unexplained death**" should be recorded on the Adverse Event eCRF. If the cause of death later becomes available (e.g., after autopsy), "unexplained death" should be replaced by the established cause of death. The term "**sudden death**" should not be used unless combined with the presumed cause of death (e.g., "sudden cardiac death").

Deaths that occur after the adverse event reporting period should be reported as described in Section 5.6.

5.3.5.8.1 Deaths due to Progression of Disease

In order to fully assess mortality as a safety endpoint, deaths due to progression of disease will be evaluated separately. Deaths that occur during the protocol-specified adverse event reporting period (see Section 5.3.1) that are attributed by the Investigator solely to the progression of disease (i.e., the qualifying stroke) will be documented and will include the investigator's assessment of the primary cause of death.

5.3.5.9 Preexisting Medical Conditions

A preexisting medical condition is one that is present at the screening visit for this study. Such conditions should be recorded on the General Medical History and Baseline Conditions eCRF.

A preexisting medical condition should be recorded as an adverse event only if the frequency, severity, or character of the condition worsens during the study. When recording such events on the Adverse Event eCRF, it is important to convey the concept that the preexisting condition has changed by including applicable descriptors (e.g., "more frequent headaches").

5.3.5.10 Progression of Acute Ischemic Stroke

Events that are clearly consistent with the expected pattern of progression of the underlying disease should not be recorded as adverse events, unless death is the outcome (see Section 5.3.5.8.1). These data will be captured as efficacy assessment data only. In most cases, the expected pattern of progression will be based on neuroimaging. If there is any uncertainty as to whether an event is due to disease progression, it should be reported as an adverse event.

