
 • To evaluate the efficacy of tenecteplase compared with placebo 	
 • Median final infarct volumes at the 72–96 hour visit or discharge (if patient is being discharged prior to 72 hours) • Median infarct growth at the 72–96 hour visit or discharge (if patient is being discharged prior to the 72–96 hour visit) • Ordinal mRS score at Day 90 by occlusion type (M1/ICA or M2 occlusions) • Ordinal mRS score at Day 30 and Day 90 by randomization site (non-endovascular capable center [nECC] or endovascular capable center [ECC]) • Proportion of patients where planned thrombectomy was not performed • Proportion of patients who are randomized at an nECC and transferred to an ECC for endovascular therapy for whom planned thrombectomy was not performed • Proportion of patients readmitted within 30 days from discharge • Proportion of patients requiring one pass with endovascular therapy device (endovascular patients only) • Mean Neuro-QoL scores by domain (Appendix 6) • Overall survival at Day 90
Safety Objective	Corresponding Endpoints

 • To evaluate the safety of tenecteplase compared with placebo 	
 • Incidence of symptomatic intracranial hemorrhage (sICH ^a) within 36 hours • Incidence and severity of adverse events • Mortality rate up to Day 30 and Day 90 • Proportion of patients with parenchymal hematoma type 2 (PH2) at the 72–96 hour visit

BI = Barthel Index; *CT* = computed tomography; *CTA* = computed tomography angiography; *ECC* = endovascular capable center; *MRA* = magnetic resonance angiography; *mRS* = modified Rankin scale; *nECC* = non-endovascular capable center; *Neuro-QoL* = Quality of Life in Neurological Disorders (scale); *NIHSS* = National Institutes of Health Stroke Scale; *sICH* = symptomatic intracranial hemorrhage; *PH1* = parenchymal hematoma type 1; *PH2* = parenchymal hematoma type 2; *TICI* = thrombolysis in cerebral infarction (scale); *T_{max}* = time to maximum of the residue function.

^a sICH is defined as ≥ 4 points of clinical worsening on the NIHSS compared with the most proximal NIHSS reported, attributed to a *bleed* on CT scan (preferred) or MRI performed within 36 hours after study drug administration.

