5.2.2 Serious Adverse Events (Immediately Reportable to the Sponsor)

A serious adverse event is any adverse event that meets any of the following criteria:

- Is fatal (i.e., the adverse event actually causes or leads to death)
- Is life threatening (i.e., the adverse event, in the view of the investigator, places the patient at immediate risk of death)
 - This does not include any adverse event that, had it occurred in a more severe form or was allowed to continue, might have caused death.
- Requires or prolongs inpatient hospitalization (see Section 5.3.5.11)
- Results in persistent or significant disability/incapacity (i.e., the adverse event results in substantial disruption of the patient's ability to conduct normal life functions)

- Is a congenital anomaly/birth defect in a neonate/infant born to a mother exposed to study drug
- Is a significant medical event in the investigator's judgment (e.g., may jeopardize the patient or may require medical/surgical intervention to prevent one of the outcomes listed above)

The terms "severe" and "serious" are not synonymous. Severity refers to the intensity of an adverse event (e.g., rated as mild, moderate, or severe, or according to *National Cancer Institute Common Terminology Criteria for Adverse Events* [NCI CTCAE]; see Section 5.3.3); the event itself may be of relatively minor medical significance (such as severe headache without any further findings).

Severity and seriousness need to be independently assessed for each adverse event recorded on the eCRF.

Serious adverse events are required to be reported by the investigator to the Sponsor immediately (i.e., no more than 24 hours after learning of the event; see Section 5.4.2 for reporting instructions).

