4.8.2 Adverse Events

All verbatim adverse event terms will be coded using the latest version of MedDRA available at the time of reporting. Adverse event severity will be graded according to National Cancer Institute Common Terminology Criteria for Adverse Events (NCI CTCAE, v5.0).

A treatment-emergent adverse event (TEAE) is defined as any new adverse event reported or any worsening of an existing condition on or after study drug administration. Adverse events with missing onset date will be considered to be treatment emergent. Adverse events with partially missing onset date will also be considered as treatment emergent when the partial date is identified to be on or later than the treatment administration date. An AE will also be considered treatment emergent if the event occurred before the start of treatment and the end date of the AE is either missing or on or after the start of treatment and AE increased in severity or either the initial or most extreme severity grade is missing. TEAEs will be tabulated by preferred terms (PT) within each system organ class (SOC) and will be presented in descending frequency.

Summaries will be provided for each of the following categories:

- All AEs
- Non-serious AEs reported in at least 5% of patient in a treatment group
- All AEs by NCI CTCAE severity

- Serious adverse events (SAEs)
- AEs related to study treatment as assessed by the investigator
- AEs leading to study discontinuation
- AEs resulting in death
- Adverse events of special interest (AESIs) as defined in the protocol (see Section 4.8.2.2)

Listings of AEs, SAEs, AESIs will also be provided.

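### Clear stroke progression is recorded as an adverse event only when fatal, and SAP 4.8.2 pools those records unflagged, so part of the AE, SAE and severity comparison reflects deaths rather than incidence

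*Protocol*

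**What the plan says.** Protocol 5.3.5.10 covers events that clearly fit the expected course of the qualifying stroke. They "should not be recorded as adverse events, unless death is the outcome". For the non-fatal ones, "These data will be captured as efficacy assessment data only". The section ends with a limit: "If there is any uncertainty as to whether an event is due to disease progression, it should be reported as an adverse event".

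Protocol 5.3.5.8 requires that all deaths in the reporting period, whatever their relation to study drug, "must be recorded on the Adverse Event eCRF and immediately reported to the Sponsor", entered as the event that caused death. A fatal event is serious under 5.2.2 and grade 5 under 5.3.3. Section 5.3.5.8.1 adds, for the assessment of mortality, that "deaths due to progression of disease will be evaluated separately", with the investigator's primary cause documented.

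Protocol 5.2.1 and 5.2.3 have hemorrhages reported whether or not they are fatal.

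"Incidence and severity of adverse events" is a named safety endpoint (Protocol 2; SAP 2.2.5 has the same). For it, SAP 4.8.2 states: "TEAEs will be tabulated by preferred terms (PT) within each system organ class (SOC) and will be presented in descending frequency". The listed summaries include all AEs, AEs by severity, SAEs and AEs resulting in death. None flags or removes progression records. SAP 4.8.2.3 separately tabulates mortality by primary cause.

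**The concern.** Two patients can have the same clear deterioration from the qualifying stroke. If one dies, the event is a grade 5 SAE. If the other survives, even severely disabled, there is no AE record at all. Whether the event is counted depends on an outcome that treatment may change.

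The affected tables are labeled and read as incidence. For clear progression they show fatal cases only, beside other terms counted in every patient who has them. If the arms differ in progression deaths, part of that difference reappears as a difference in SAE incidence, even when progression is equally frequent in both arms. Deaths, SAEs and non-serious AEs are also among the data summarized at the safety interims (Protocol 6.6.1), so the data monitoring committee would read the same tables.

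**Working it through.** **The plan's own figure.** The concern attacks no stated number, but the illustration uses the Day 90 mRS distributions in Protocol Table 7, so these were checked against the stated power.
- Chance that a tenecteplase patient does better than a placebo patient, ties counted half: 0.58955.
- Null standard error with 216 per arm (432 evaluable): √[(1 − Σp̄³)/12 × 2/216] = √[(1 − 0.0216)/12 × 2/216] = 0.0275.
- Power at two-sided 0.049: Φ(0.08955/0.0275 − 1.969) = 90.2%. With the variance under the alternative it is 90.5%. Whitehead's formula at a common odds ratio of 1.76 gives 91.6%.

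The stated power of at least 90% reproduces.

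**Inputs for the size of the effect.**
- Deaths (mRS 6) in Table 7: 12% tenecteplase, 18% placebo. Of 228 per arm: 0.12 × 228 = 27.4 and 0.18 × 228 = 41.0.
- f, the share of deaths due solely to clear progression. The documents give no value, so it is an assumption, equal in both arms.
- q, the share of those patients who already have another recorded SAE and so are in the any-SAE count anyway. Also an assumption, equal in both arms.

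**Formula.** Difference in any-SAE incidence created by the recording rule = (18% − 12%) × f × (1 − q).

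| f | q = 0 | q = 0.25 | q = 0.5 | q = 0.75 |
|---|---|---|---|---|
| 1 | 6.0 | 4.5 | 3.0 | 1.5 |
| 0.75 | 4.5 | 3.4 | 2.25 | 1.1 |
| 0.5 | 3.0 | 2.25 | 1.5 | 0.75 |
| 0.25 | 1.5 | 1.1 | 0.75 | 0.4 |

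Entries are percentage points lower on tenecteplase. The maximum is 0.06 × 228 = 13.7 patients; the minimum shown is 0.06 × 228 × 0.25 × 0.25 = 0.9 patients.

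**Cross-check with equal true progression.** Suppose 40% of each arm has progression, 20% has some other SAE independently, and f = 0.5.
- Recorded any-SAE, tenecteplase: 1 − (1 − 0.06)(1 − 0.20) = 24.8%.
- Recorded any-SAE, placebo: 1 − (1 − 0.09)(1 − 0.20) = 27.2%.
- If all progression were counted: 1 − (1 − 0.40)(1 − 0.20) = 52.0% in both arms.

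The recorded gap of 2.4 points comes entirely from the rule. It equals the formula at q = 0.2: 6 × 0.5 × 0.8 = 2.4.

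**Rows and other tables.** Overlap with other SAEs dilutes the any-SAE total but not the preferred-term rows. With f = 0.6, fatal progression is 7.2% against 10.8% (16.4 against 24.6 of 228). The ratio of 0.67 is simply 12/18 for any common f. It describes the fatal-progression component and is not a relative risk of SAE incidence. Any-AE incidence would move less than any-SAE incidence, because every patient with another SAE, and others besides, already has an AE. In the severity table, clear progression can appear only as grade 5.

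**The case against.** The strongest reply is that the rule is narrow and the information is largely available elsewhere. Uncertain deterioration goes on the AE form whether or not it is fatal, and hemorrhage, the main harm of a thrombolytic, lies outside the rule. Mortality is tabulated by primary cause, AEs resulting in death have their own summary, and non-fatal progression should show in NIHSS, infarct growth and the ordinal mRS. Safety is descriptive, with no hypothesis tests (SAP 4.8).

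All of that stands, and it limits the size and consequence of the point. It does not correct the tables themselves: no listed summary lets a reader see AE, SAE or severity incidence without the outcome-dependent records. Having no tests does not help, because the descriptive tables are the whole AE comparison.

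A reader might infer more than the documents support:
- *The SAE table repeats the whole mortality difference.* This needs every death to be solely from progression and no such patient to have another SAE.
- *The tables will flatter tenecteplase.* The 12% and 18% are planning assumptions. If tenecteplase had more progression deaths, the same rule would make its SAE count look worse.
- *Worse true progression on tenecteplase would still look better.* An example with 30% against 25% true progression and 7.2% against 10.8% fatal implies case fatality of 7.2/30 = 24% against 10.8/25 = 43%. Nothing in the documents supports that gap.
- *The SAP breaks the promise in Protocol 5.3.5.8.1.* That section concerns the assessment of mortality, and SAP 4.8.2.3 meets it with the tabulation by primary cause. It says nothing about AE tables.
- *SAE statements should rest only on the version without these events.* That would take deaths out of the headline figure on an investigator's attribution, and it would still not give the incidence of progression, because survivors' clear progression stays off the form.

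**Conclusion.** The point holds for clear progression of the qualifying stroke. For those events, the all-AE, SAE and severity tables reflect deaths rather than incidence, and the SAE comparison shifts toward the arm with fewer progression deaths.

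Under the plan's assumed mortality, the artificial difference in any-SAE incidence cannot exceed 6.0 points. It is about 0.4 to 3 points for f of 0.25 to 0.5 and q of 0 to 0.75. These values of f and q are assumptions, taken equal across arms, and the sign depends on the mortality actually observed. The effect is confined to descriptive safety tables. The primary analysis, the type I error rate, all-cause mortality and sICH monitoring are unaffected. The change should be made because it makes a named safety endpoint interpretable at little cost.

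**What to change.** In SAP 4.8.2:
- Flag AE records that the investigator attributes solely to progression of the qualifying stroke, using the attribution already documented under Protocol 5.3.5.8.1.
- Show the flagged records in a separate row labeled *recorded only if fatal*.
- Present any-AE, SAE and by-severity incidence by arm both with and without them, side by side, with neither version replacing the other.
- Keep all-cause mortality counting every death.

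The cost is one flag and one extra version of three descriptive tables. No new data are collected, and the recording rule in the protocol need not change. The flag rests on investigator attribution, and the version without these events does not estimate how often progression occurs; a table footnote should say both.

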5.3.5.11 Hospitalization or Prolonged Hospitalization

Any adverse event that results in hospitalization (i.e., inpatient admission to a hospital) or prolonged hospitalization should be documented and reported as a serious adverse event (per the definition of serious adverse event in Section 5.2.2), except as outlined below.

An event that leads to hospitalization under the following circumstances should not be reported as an adverse event or a serious adverse event:

- Planned hospitalization required by the protocol (e.g., for study drug administration or insertion of access device for study drug administration)
- Hospitalization for a preexisting condition, provided that all of the following criteria are met:
 - The hospitalization was planned prior to the study or was scheduled during the study when elective surgery became necessary because of the expected normal progression of the disease
 - The patient has not experienced an adverse event

An event that leads to hospitalization under the following circumstances is not considered to be a serious adverse event, but should be reported as an adverse event instead:

- Hospitalization that was necessary because of patient requirement for outpatient care outside of normal outpatient clinic operating hours

5.3.5.12 Reporting Requirements for Cases of Accidental Overdose or Medication Error

Accidental overdose and medication error (hereafter collectively referred to as "special situations"), are defined as follows:

- Accidental overdose: accidental administration of tenecteplase in a quantity that is 10% greater than the assigned dose
- Medication error: accidental deviation in the administration of tenecteplase
- In some cases, a medication error may be intercepted prior to administration of tenecteplase

Special situations are not in themselves adverse events, but may result in adverse events. All special situations associated with tenecteplase, regardless of whether they

result in an adverse event, should be recorded on the Adverse Event eCRF as described below:

- Accidental overdose: Enter "tenecteplase" and "accidental overdose" as the event term. Check the "Accidental overdose" and "Medication error" boxes.
- Medication error that does not qualify as an overdose: Enter "tenecteplase" and a description of the error (e.g., wrong dose administered, wrong dosing schedule, incorrect route of administration, wrong drug, expired drug administered) as the event term. Check the "Medication error" box.
- Medication error that qualifies as an overdose: Enter "tenecteplase" and "accidental overdose" as the event term. Check the "Accidental overdose" and "Medication error" boxes. Enter a description of the error in the additional case details.
- Intercepted medication error: Enter "tenecteplase" and "intercepted medication error" as the event term. Check the "Medication error" box. Enter a description of the error in the additional case details.

Each adverse event associated with a special situation should be recorded separately on the Adverse Event eCRF. If the associated adverse event fulfills seriousness criteria, the event should be reported to the Sponsor immediately (i.e., no more than 24 hours after learning of the event; see Section 5.4.2). Adverse events associated with special situations should be recorded as described below for each situation:

- Accidental overdose: Enter the adverse event term. Check the "Accidental overdose" and "Medication error" boxes.
- Medication error that does not qualify as an overdose: Enter the adverse event term. Check the "Medication error" box.
- Medication error that qualifies as an overdose: Enter the adverse event term. Check the "Accidental overdose" and "Medication error" boxes.

As an example, an accidental overdose that resulted in a headache would require the completion of two Adverse Event eCRF pages, one to report the accidental overdose and one to report the headache. The "Accidental overdose" and "Medication error" boxes would need to be checked on both eCRF pages.

5.4 IMMEDIATE REPORTING REQUIREMENTS FROM INVESTIGATOR TO SPONSOR

Certain events require immediate reporting to allow the Sponsor to take appropriate measures to address potential new risks in a clinical trial. The investigator must report such events to the Sponsor immediately; under no circumstances should reporting take place more than 24 hours after the investigator learns of the event. The following is a list of events that the investigator must report to the Sponsor within 24 hours after learning of the event, regardless of relationship to study drug:

- Serious adverse events (defined in Section 5.2.2; see Section 5.4.2 for details on reporting requirements)

- Adverse events of special interest (defined in Section 5.2.3; see Section 5.4.2 for details on reporting requirements)
- Pregnancies (see Section 5.4.3 for details on reporting requirements)

The investigator must report new significant follow-up information for these events to the Sponsor immediately (i.e., no more than 24 hours after becoming aware of the information). New significant information includes the following:

- New signs or symptoms or a change in the diagnosis
- Significant new diagnostic test results
- Change in causality based on new information
- Change in the event's outcome, including recovery
- Additional narrative information on the clinical course of the event

Investigators must also comply with local requirements for reporting serious adverse events to the local health authority and IRB/EC.

